**Research Question(s):**

Primary: Does lidocaine versus saline as a steroid diluent affect objective upper extremity strength following cervical epidural steroid injection in patients being treated for cervical radicular pain?

Secondary: Does lidocaine versus saline as a steroid diluent affect short-term pain, function, medication use, and global impression of change outcomes of cervical epidural injection for the treatment of radicular pain?

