**Null Hypothesis:**

1. Cervical epidural steroid injections that include local anesthetic as a diluent have no effect on objective upper extremity strength following the injection.
2. Cervical epidural steroid injections for radicular pain that include lidocaine compared to saline as a diluent do not improve short-term pain, function, medication use, and global impression of change outcomes.

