## **Participant Recruitment**

Our intended subject demographic includes an active population between the ages of 18 and 80 years on the day of enrollment. We intend to recruit participants primarily through word-of-mouth and from a database or participant pool for which participants have given prior permission to be contacted for research studies. Additionally, recruiting will take place through the distribution of flyers to the Health Sciences Education Building, University of Utah Student Life Center, the University of Utah South Jordan Health Center, the University of Utah Orthopaedic Center, and the University of Utah hospital. Upon first contact with the potential participant, the study coordinator or research associate will provide a basic description of the study and review inclusion and exclusion criteria, general health status, and past and current athletic participation. Interested volunteers who qualify will be asked to report to the University of Utah Orthopaedic Center. Prior to screening procedures and after being informed of any potential risks involved in the study, volunteers will be asked to provide written, informed consent for study participation.

Inclusion criteria:

- 1) Age 18-80.
- 2) Clinical diagnosis of cervical radicular pain.
- 3) Magnetic resonance imaging pathology consistent with clinical symptoms/signs.
- 4) Numerical Rating Scale (NRS) pain score of 4 or higher.
- 5) Pain duration of more than 6 weeks despite trial of conservative therapy (medications, physical therapy, or chiropractic care).
- 6) Patients who will undergo CESI for treatment of cervical radiculitis.

Exclusion criteria:

- 1) Refusal to participate, provide consent, or provide communication and follow-up information for duration of the study.
- 2) Inability to perform handgrip or arm strength testing.
- 3) Contraindications to Cervical ESI (active infection, bleeding disorders, current anticoagulant or antiplatelet medication use, allergy to medications used for CIESI, and pregnancy).
- 4) Cervical spinal cord lesions; cerebrovascular, demyelinating, or other neuro-muscular muscular disease.
- 5) Patient request for or requirement of conscious sedation for the injection procedure.

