For Group 1 and Group 2, patients will be randomized to treatment group based on a random computer-generated schedule. Participants will be blinded to the group to which they are randomized. All standard procedures for CESIs will be followed as is standard practice including time out, skin prep, hemodynamic monitoring, image guidance, etc.

Per randomization, triamcinolone acetonide 80 mg (Kenalog) (E. R. Squibb & Sons Limited, Uxbridge UK) will be combined with 2mL Lidocaine 1% or 2 mL preservative free saline and will be injected during the CESI procedure. In all cases, the total injectate volume will be 4 mL. All injections will be image guided with fluoroscopy, as is the current standard practice. Fluoroscopy time will be recorded.

The participant will be discharged from the clinic with written discharge instructions (current standard practice).

Participants will be telephoned and emailed by clinic personnel 1 day after the CESI to assess for subjective weakness in the hands or arms as well as any other adverse reactions. As above, the UEFI will be administered at this time.

Participants will only be recruited for this study for a single CESI. Those who require repeat injections will not be recruited a second or third time.

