### **Data Collection:**

#### **1 Data evaluation (See Case report form)**

#### **2 Interpretation of Anticipated Results:**

### **Statistical analysis**

Differences in strength as measured by dynamometry pre-and post-injection will be assessed by Fishers exact test.

Means and standard deviations of subject demographic data, as well as pain scores and UEFI scores will be calculated.

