### **Data Analysis Plan**

The primary outcome will be the proportion of participants with 50% or greater reduction in neck and arm pain on the NRS pain score at the 1-month follow-up assessment. Secondary outcomes included reduction in median NRS pain score (both neck pain and arm pain), NDI-5, MQS III, opioid consumption in daily morphine equivalents, PGIC score, and satisfaction score. Secondary outcomes will also be defined based on categorical “responder analysis” definitions of important clinical change given the National Institutes of Health recommendation for responder analysis in the assessment of therapeutic spine pain interventions. The responder analysis will include the proportion of patients with 30% or greater improvement on the NDI-5, a PGIC score less than 3 (indicating “improved” or “very much improved”), a 6.8 or greater point reduction on the MQS III score (equivalent to approximately 10 daily morphine equivalents), and the proportion of participants who undergo surgical spine surgery.

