### **Secondary outcomes:**

- Change in mean arterial pressure prior to, 30 minutes after CESI, via automated blood pressure cuff measure.
- Change in HR prior to, 30 minutes after CESI
- Change in NRS pain score from pre-injection to post injection (immediate) and 1-day.
- Change in UEFI score from pre-injection to post injection (immediate) and 1-day.
- Change in pain medication use from pre-injection to post injection (immediate) and 1-day.
- Procedure complications or adverse reactions to medications used

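### The plan states no between-arm estimate, interval or test for its second null hypothesis (pain, function, medication use, global impression of change)

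*Combined protocol and SAP*

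**What the plan says.** All references are to the combined protocol and SAP.

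- **Research Question(s)** asks: "Secondary: Does lidocaine versus saline as a steroid diluent affect short-term pain, function, medication use, and global impression of change outcomes".
- **Null Hypothesis**, item 2, is that injections with "lidocaine compared to saline as a diluent do not improve short-term pain, function, medication use, and global impression of change outcomes". Both statements compare the two arms.
- **Statistical analysis** assigns Fisher's exact test to strength, described as a pre- and post-injection difference. For the rest it says: "Means and standard deviations of subject demographic data, as well as pain scores and UEFI scores will be calculated". Medication use and global impression of change do not appear there.
- **Data Analysis Plan** says: "The primary outcome will be the proportion of participants with 50% or greater reduction in neck and arm pain on the NRS pain score", assessed at 1 month. It then lists further outcomes (median NRS reduction, NDI-5, MQS III, opioid dose, PGIC, satisfaction) and responder definitions: at least 30% improvement on NDI-5, PGIC below 3, at least 6.8 points on MQS III, and surgery. It names no effect measure, interval or test.
- **Secondary outcomes** lists change scores, for example "Change in NRS pain score from pre-injection to post injection (immediate) and 1-day", and the same for UEFI and medication use. No method is given.
- **Power Analysis** and **Primary outcome** concern strength: 52 per arm, Fisher's exact test, 20% deficit with lidocaine, none with saline apart from a 2% measurement error, and a 19.5% threshold for the categorical analysis.

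**The concern.** A hypothesis about a difference between arms needs a between-arm estimate with its uncertainty. The stated analysis of pain and UEFI is descriptive, and two of the four domains have no stated analysis at all. One of the two numbered hypotheses therefore cannot be judged from the analyses in the plan, and the method could be settled after the data are seen.

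There is also a wording defect on strength. Read literally, Fisher's test is applied to pre- and post-injection values. These are paired within participants, and Fisher's test for two independent groups does not fit them.

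**Working it through.** **1. Where a method is stated**

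| Domain | Outcome defined | Time point given | Between-arm method |
|---|---|---|---|
| Pain (NRS) | Change; at least 50% reduction; median reduction | Immediate and 1 day; 1 month for the 50% outcome | None (means and SDs) |
| Function | UEFI change; NDI-5 score and responder | Immediate and 1 day for UEFI; none attached to NDI-5 | None (means and SDs for UEFI only) |
| Medication use | Change; MQS III score and responder; opioid dose | Immediate and 1 day for change; none attached to MQS III or opioid dose | None |
| Global impression | PGIC score; PGIC below 3 | None attached | None |
| Strength | Change; 19.5% threshold | 30 minutes | Fisher's exact test |

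Outcomes and several time points are fixed. What is missing is the comparison.

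**2. The plan's own figure (strength)**

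Inputs from Power Analysis: 52 per arm, 20% against 2% (the measurement error used as the saline rate), nominal alpha 0.05. Sidedness is not stated; two-sided is used here. All outcomes of two Binomial(52, p) arms are enumerated, and the probabilities of those with Fisher p ≤ 0.05 are summed.

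- Power at 20% against 2%: 0.803 (stated: above 80%).
- Size at 2% against 2%: 0.00042 (stated: 0.0004).

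Both figures reproduce when the test is a comparison of arms. This supports reading the strength analysis as between-arm, despite the pre/post wording.

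**3. Cost of leaving the method open for one change outcome**

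Assumptions, since the documents give no values: normal data, equal SD before and after, correlation r between baseline and follow-up, and no true effect. Two analyses are compatible with a change outcome: the change score Y − X and ANCOVA, which is in effect Y − rX.

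- Var(Y − X) = 2(1 − r); Var(Y − rX) = 1 − r²; their covariance is 1 − r².
- The correlation of the two test statistics is therefore √((1 + r)/2) = 0.806, 0.866, 0.922 at r = 0.3, 0.5, 0.7.
- Chance that at least one gives two-sided p < 0.05 (bivariate normal): 7.8%, 7.3%, 6.8%, against 5% for a single fixed analysis.

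**4. Precision of the missing comparison**

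The basic 95% half-width is t × √(2/52) = 1.983 × 0.1961 = 0.389 SD, where SD is that of a single measurement. Multiply by √(2(1 − r)) for the change score and by √(1 − r²) for ANCOVA.

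| r | Change score | ANCOVA |
|---|---|---|
| 0.3 | 0.46 SD | 0.37 SD |
| 0.5 | 0.39 SD | 0.34 SD |
| 0.7 | 0.30 SD | 0.28 SD |

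For responder proportions the half-width is 1.96 × √(2p(1 − p)/52): 0.176 at p = 0.3, 0.188 at 0.4 and 0.192 at 0.5, or 18 to 19 percentage points at these assumed rates.

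**The case against.** **The question is secondary.** Research Question(s) labels it so, and the trial is powered for strength. This stands, and it limits the severity. It does not remove the gap, because the question is also a numbered null hypothesis and descriptive statistics cannot test it.

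**Means, SDs and numbers by arm would let a reader compute a difference and interval.** This is partly true. Such tables give an unadjusted comparison at a given time point. But the plan does not say that the summaries are by arm, does not commit to the contrast, and does not mention medication use or global impression.

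**Fisher's test is implied for the responder proportions.** No section says so, and it would not cover the scores.

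**ANCOVA over the change score is partly preference.** A change-score analysis fixed in advance would also close the gap. ANCOVA uses the same data and is never less precise in the table above; the gain is small at r = 0.7 and larger at r = 0.3.

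A reader might infer more than the documents support:

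- *That arm means would mislead because everyone enters with a "Numerical Rating Scale (NRS) pain score of 4 or higher" and receives the same steroid.* These influences act equally on both randomised arms and cancel in the difference. They would defeat only a within-arm before-after inference, which the plan does not propose for pain.
- *That the false-positive rate is 9% to 10%, as it is when a follow-up-only analysis is added to the choice.* The Secondary outcomes section specifies change for NRS and UEFI, so that third option is not supported for them.
- *That every measure is a separate, equal chance of success.* The Data Analysis Plan does single out one outcome, the 1-month pain responder proportion. Its conflict with the strength primary is a different defect.

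**Conclusion.** The gap is real and can be confirmed by reading: no section gives a between-arm estimate, interval or test for pain, function, medication use or global impression of change. This conclusion needs no numerical assumption. Its scale does: under the assumed normal data and r from 0.7 to 0.3, an open choice between change score and ANCOVA raises the false-positive rate for one outcome from 5% to about 7% to 8%, a moderate inflation.

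A reader might conclude that the main strength comparison is unsound. The documents do not support that: Power Analysis and Primary outcome describe a between-arm categorical comparison, and the stated power and size reproduce on that reading. Only the pre/post wording needs repair.

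This should be fixed, as a defect in the analysis of a secondary hypothesis. That the Data Analysis Plan gives the label of primary to a pain outcome, while the research question, power calculation and Primary outcome section concern strength, is a separate and more serious point and should not be counted here.

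**What to change.** 1. **Strength.** Reword Statistical analysis so that the proportion with a fall in strength of at least 19.5% at 30 minutes is compared between lidocaine and saline by Fisher's exact test, with the risk difference and 95% CI.
2. **NRS and UEFI.** Replace the means-and-SDs sentence for these scores with the between-arm difference and 95% CI from ANCOVA adjusted for the baseline already collected, at each time point actually collected. Make this the single analysis of these scores.
3. **Other outcomes.** For the responder outcomes in the Data Analysis Plan, including surgery, report the between-arm risk difference with 95% CI. For the remaining scores, fix one method in advance: baseline-adjusted where a baseline exists, and a rank-based difference for the ordinal PGIC. Do not choose after inspecting skewness.
4. **One test.** Name one outcome and time point as the test of the second null hypothesis. Report all others as estimates with intervals and no test.
5. **Reconcile.** Align the primary outcome in the Data Analysis Plan with the strength primary elsewhere. Align the time points in the Data Analysis Plan and Secondary outcomes with the assessments in Procedure.

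**Cost.** For strength and for UEFI at baseline and 1 day: SAP wording and a few lines of code, with no new data. For the rest, collection must be confirmed first. Procedure schedules a contact "1 day after the CESI to assess for subjective weakness in the hands or arms as well as any other adverse reactions", with the UEFI added, but lists no NRS or medication question at that contact, no immediate post-injection UEFI and no 1-month assessment. The report form is not available here and may cover some of these.

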### **Data Storage**

Hard copy data will be collected and stored in a password-protected computer located in the Division of PM&R. Subjects will each be assigned an ID number that will be used as the sole identifier on any documents. Subject data will be compiled onto a single password protected file, where they will only be identified by their ID number. An enrollment log will be the only file where subject names are correlated with ID numbers. This will be kept in a separate, secure, password-protected file in the Division of PM&R.

### **Data Analysis Plan**

The primary outcome will be the proportion of participants with 50% or greater reduction in neck and arm pain on the NRS pain score at the 1-month follow-up assessment. Secondary outcomes included reduction in median NRS pain score (both neck pain and arm pain), NDI-5, MQS III, opioid consumption in daily morphine equivalents, PGIC score, and satisfaction score. Secondary outcomes will also be defined based on categorical “responder analysis” definitions of important clinical change given the National Institutes of Health recommendation for responder analysis in the assessment of therapeutic spine pain interventions. The responder analysis will include the proportion of patients with 30% or greater improvement on the NDI-5, a PGIC score less than 3 (indicating “improved” or “very much improved”), a 6.8 or greater point reduction on the MQS III score (equivalent to approximately 10 daily morphine equivalents), and the proportion of participants who undergo surgical spine surgery.

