### **Power Analysis**

Statistical Plan & Sample Size Calculation:

Size of study groups:

Group 1: n = 52

Group 2: n = 52

A power analysis was performed based upon previous observations of UE strength (28) using Fisher's Exact Test. Sample sizes of 52 in each of the two treatment groups will achieve > 80% power to detect a group different in proportions, assuming 20% of patients in the Lidocaine group will demonstrate a motor deficit after the CESI and those in the Saline group will demonstrate no difference in motor strength after the CESI, assuming a 2% measurement error with the strength testing method described. The alpha level of this test statistic is set at 0.05, but the significance level actually achieved by this study design is 0.0004.

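### The NRS pain outcome is worded as a fall in the group median and has no between-arm estimator; a baseline-adjusted mean difference would be clearer and more precise

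*Combined protocol and SAP*

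**What the plan says.** Three sections touch on the NRS summary.

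- **Data Analysis Plan:** "Secondary outcomes included reduction in median NRS pain score (both neck pain and arm pain"). This follows a responder proportion for "reduction in neck and arm pain on the NRS pain score at the 1-month follow-up assessment". The median outcome has no time point of its own.
- **Secondary outcomes:** "Change in NRS pain score from pre-injection to post injection (immediate) and 1-day". No summary statistic is given, and neck and arm pain are not separated.
- **Statistical analysis:** "Means and standard deviations of subject demographic data, as well as pain scores and UEFI scores will be calculated". This describes the data; it is not a comparison of arms.

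The only named test is Fisher's exact test, and it is tied to strength. The Research Question(s) and Null Hypothesis sections nevertheless ask whether lidocaine rather than saline changes short-term pain. The Procedure section records an NRS score before the injection, so a baseline value exists.

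**The concern.** A comparative question about pain needs one stated contrast between arms, and the plan has none. The one phrase that comes close is built on a group median. Its literal reading is the median before minus the median after, which is not a summary of how much patients changed. It makes no use of the correlation between a patient's two scores, and on a whole-number scale it moves almost only in whole-point steps.

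Two things are at stake. The analyst could choose the summary after seeing the data. And if the median wording is followed, a real difference of modest size may often be reported as none.

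**Working it through.** **Plan's own figure.** The documents give no NRS figure to reproduce. The only stated calculation is for strength: "Sample sizes of 52 in each of the two treatment groups will achieve > 80% power", "assuming 20% of patients in the Lidocaine group will demonstrate a motor deficit" and "assuming a 2% measurement error with the strength testing method described". Exact enumeration of the two-sided Fisher test with 52 per arm gives power 0.803 at 20% against 2%, and size 0.00042 at 2% against 2%. Both agree with the plan (over 80%, and 0.0004). Nothing below alters them.

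**Do the summaries differ?** With complete data, mean(before − after) = mean(before) − mean(after) exactly. Means of scores and mean change therefore give the same arm difference. Medians have no such identity. A three-patient example:

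- Baselines 4, 6, 8 and follow-ups 8, 4, 6.
- Median before minus median after = 6 − 6 = 0.
- Individual changes are −4, 2, 2, so their median is 2 and their mean is 0.

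In simulated trials with near-symmetric scores, the arm difference by means and by reduction in medians differed by at most 0.18 NRS points. In an assumed responder mixture (60% against 40% responders, who fall to about 1.5 while the others fall about 0.5) the results were:

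| Summary | 60% responders | 40% responders | Arm difference |
|---|---|---|---|
| Mean change | 3.23 | 2.33 | 0.91 (before rounding) |
| Reduction in median | 5 | 3 | 2 |
| Median of changes | 3 | 1 | 2 |

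**Precision by large-sample normal theory** (continuous scores, equal SDs, pre/post correlation r, n per arm), for one arm:

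- Var(mean change) = 2·SD²·(1 − r)/n.
- Var(median before − median after) = (π/2)·2·SD²·[1 − (2/π)·asin(r)]/n.
- Ratio = (π/2)·[1 − (2/π)·asin(r)]/(1 − r).
- r = 0.3: 1.571 × 0.806/0.7 = 1.81.
- r = 0.6: 1.571 × 0.590/0.4 = 2.32.

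**Precision by simulation, against the baseline-adjusted mean difference.** From the documents: 52 per arm, and entry at "Numerical Rating Scale (NRS) pain score of 4 or higher". Assumed: baseline mean 6 to 7, SD 1.6; saline follow-up mean 4.5, SD 2.5; r from 0.3 to 0.6; true benefit 1 point; scores limited to 0-10.

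| Quantity | Continuous | Whole-number |
|---|---|---|
| Variance ratio, reduction in median | 2.0 to 2.3 | 3.0 to 4.3 |
| P(estimate zero or reversed), reduction in median | 3 to 7% | 19 to 24% |
| Same probability, adjusted difference | about 1 to 2% | about 1 to 2% |

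If the phrase means the median of individual changes, the variance ratio is 1.6 to 3.3 across both kinds of score.

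In patients, 52 per arm analysed by reduction in median carries the information of about 52/2.3 = 23 to 52/2.0 = 26 per arm (continuous), or 52/4.3 = 12 to 52/3.0 = 17 per arm (whole-number), analysed by the adjusted difference.

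**Sensitivity.** With whole-number scores the ratio depends on where the means fall between integers. With baseline mean 6.5 and saline follow-up mean from 3.5 to 5 it was 3.6 to 5.0. Against mean change, over a wider set of assumed means, SDs and correlations (0.2 to 0.7), it ran from 1.3 to 10.8 for whole-number scores and 1.7 to 2.7 for continuous ones.

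**The case against.** A reader might infer that the three sections give three conflicting definitions with three different arm differences. The documents do not support that. The Statistical analysis sentence is descriptive and also covers demographics and UEFI. The Secondary outcomes entry names no summary; wording about each individual appears only for strength, in the Primary outcome section. If that entry is summarised by a mean, it agrees exactly with the means. The sections also appear to concern different times: immediate and 1 day in one, a 1-month primary in the other. So part of the difference may be one of time point.

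A reader might also infer a fixed penalty of about four times the variance. No NRS mean, SD, correlation or scoring unit is given, and the ratio moves widely with what is assumed. Only a range with its assumptions can be stated.

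The median phrase may be loose wording for the median of individual changes. The pairing criticism then falls away and the loss is smaller, though it does not vanish. Pairing is also not the whole story, since the point estimate of a mean change does not depend on it either; the gain comes from using the baseline correlation.

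Finally, medians are a legitimate choice for a bounded ordinal score, and the outcome is secondary. That stands as a limit on how much this matters. It does not supply the missing between-arm estimator.

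**Conclusion.** The point holds in limited form. The plan words one NRS outcome as a reduction in a group median, leaves the other without a summary, and names no between-arm estimator for a question that is comparative. The literal median measure is less precise than a baseline-adjusted mean difference in every scenario run: about 2.0 to 2.3 times the variance for continuous scores and 3.0 to 4.3 times for whole-number scores, or 1.6 to 3.3 times on the milder reading. These figures rest on the assumed values listed above and would change with the real score distribution. In near-symmetric data the harm is mainly lost precision; in responder-type data the size of the reported effect can change as well. The sample size rests on strength, so the stated power is unaffected. This is a cheap, worthwhile improvement to a secondary outcome and not a threat to the trial's main result.

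**What to change.** In the Data Analysis Plan, replace the group-median wording with the lidocaine-minus-saline mean difference in follow-up NRS, adjusted for baseline NRS, with a 95% confidence interval. State it at each time point the plan names: immediate and 1 day (Secondary outcomes) and 1 month (Data Analysis Plan). Analyse neck and arm pain separately where both are recorded. Use the same definition for the NRS entry under Secondary outcomes. Label the means and SDs in the Statistical analysis section, and any medians and interquartile ranges, as descriptive.

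The cost is wording only, because a pre-procedure NRS score is already recorded. The downside is that a mean is slightly more sensitive to skewed scores than a median, a small matter on a bounded 0-10 scale.

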### **Procedure**

All patients evaluated in the University of Utah Orthopaedic Center who will have a CESI with triamcinolone will be considered for participation in the study. Subjects will be consented for participation in the study and informed consent will be obtained. Each subject will be randomized into a group assignment in a 1:1 manner, #1 or #2, as outlined in the Methods section above. All documentation will be stored using a unique coded identifier to ensure compliance with HIPPA.

A Report Form will be used to record all pre- and post-procedure data (See Appendix)

In every participant in Control Cohort, Group 1 and Group 2, a pre-procedure NRS pain score, pain medication use, and presence of subjective or objective symptoms of UE weakness will be recorded. Bilateral handgrip, wrist extension, elbow flexion, and elbow extension strength (myotomes C5-T1) will be measured by a trained research assistant prior to the injection procedure using a handheld JAMAR® PLUS+ digital dynamometer (Sammons Preston, Bollingbrook, IL) for hand grip strength and a Lafayette Manual Muscle Testing System model 01163 (Lafayette Instrument Company, Lafayette, IN) for arm strength assessment. Three baseline strength measurements will be recorded for each strength test (20,21). Validation studies using similar protocols for upper extremity functional strength measurement show a high degree

of test-retest reliability with a narrow range of variability [22–26]. Additionally, light touch and pinprick sensory testing in the C5-T1 dermatomes will be performed with a tapered whisp of cotton and a disposable safety pin, respectively, in accordance with the methods described when performing an American Spinal Injury Association (ASIA) examination in accordance with the international standards for neurological classification of spinal cord injury (27).

Measurements will be taken prior to and 30 minutes following the injection procedure. Participants in Group #1 and Group #2 will also be queried with the Upper Extremity Functional Index (UEFI) before the injection procedure and again 1 day after the procedure (administered via telephone).

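### The Data Analysis Plan relies on a 1-month follow-up, an NDI-5 baseline and neck and arm pain scores that the Procedure does not schedule; a missed NDI-5 baseline cannot be obtained after injection

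*Combined protocol and SAP*

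**What the plan says.** **Outcomes.** The Data Analysis Plan calls its lead outcome primary: the "proportion of participants with 50% or greater reduction in neck and arm pain on the NRS pain score at the 1-month follow-up assessment". Its secondary outcomes are median NRS reduction for neck and for arm pain, NDI-5, MQS III, daily morphine equivalents, PGIC and satisfaction. The responder definitions follow: "The responder analysis will include the proportion of patients with 30% or greater improvement on the NDI-5", "a PGIC score less than 3", "a 6.8 or greater point reduction on the MQS III score (equivalent to approximately 10 daily morphine equivalents", "and the proportion of participants who undergo surgical spine surgery". Only the lead outcome carries a time point.

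**Data collection.** Before injection, the Procedure says that "a pre-procedure NRS pain score, pain medication use, and presence of subjective or objective symptoms of UE weakness will be recorded", together with dynamometry, sensory testing and the UEFI. On timing it says: "Measurements will be taken prior to and 30 minutes following the injection procedure". The last contact is on day 1: "Participants will be telephoned and emailed by clinic personnel 1 day after the CESI to assess for subjective weakness in the hands or arms", along with adverse reactions and the UEFI.

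**Other outcome lists.** The Primary outcome section gives change in strength at 30 minutes. The Secondary outcomes section covers blood pressure, heart rate, NRS, UEFI, medication use and complications, and its latest time point is 1 day. The Statistical analysis section mentions only strength, demographics, pain scores and UEFI.

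**The concern.** The outcomes and the schedule do not match. A site that follows the Procedure would finish with each participant on day 1 and would have nothing from which to compute an outcome that the Data Analysis Plan labels primary.

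A late amendment can repair only part of this. Outcomes that need follow-up alone can be rescued by adding a contact for participants not yet past 1 month. Outcomes defined as change from baseline cannot be rescued if the baseline instrument was not given before injection. A score recalled afterwards may be coloured by relief already felt, and no analysis method restores the missing value. Each participant injected without the questionnaire adds to that loss.

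**Working it through.** The check consists of setting each outcome in the Data Analysis Plan against what the Procedure schedules.

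| Outcome | Needs baseline? | Baseline listed in Procedure | Follow-up after day 1 in Procedure |
|---|---|---|---|
| NRS, neck and arm (50% response; median change) | Yes | One NRS score, neck and arm not separated | None |
| NDI-5 (30% response) | Yes | None; the UEFI is a different instrument | None |
| MQS III (6.8-point reduction) | Yes | Medication use, content unspecified | None |
| Daily morphine equivalents | For change | Medication use, content unspecified | None |
| PGIC (below 3) | No | Not needed | None |
| Satisfaction | No | Not needed | None |
| Spine surgery | No | Not needed | None; no time horizon given |

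1. **Follow-up.** None of the seven rows has a scheduled collection after day 1. The 1-month time point appears in the Data Analysis Plan and nowhere else. NDI-5, MQS III, PGIC and satisfaction scores are likewise named only there.

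2. **Baselines.** NDI-5 has none. The NRS has one, but the Data Analysis Plan refers to both neck pain and arm pain, so a single score may not support the response rule. MQS III and morphine equivalents can be scored later if the medication record holds drug, dose and frequency; the Procedure does not say whether it does.

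3. **The second null hypothesis.** It names four domains: pain, function, medication use and global impression of change. The first three have day-1 outcomes in the Secondary outcomes section (NRS, UEFI, medication use). Global impression of change has no measure outside the Data Analysis Plan. So one domain of four depends wholly on that section.

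4. **Which endpoint the sample size serves.** The Power Analysis states more than 80% power with 52 per group, 20% with a motor deficit on lidocaine, a 2% measurement error on saline, Fisher's exact test at 0.05, and an attained level of 0.0004. Sidedness is not stated; I assume a two-sided test and read the 2% as the saline event rate.
   - Power = Σ Bin(x; 52, 0.20) × Bin(y; 52, 0.02) over all (x, y) with Fisher p ≤ 0.05 = 0.803 (0.791 with 51 per group).
   - Size at a common rate of 2% = 0.00042.

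   Both stated figures reproduce. The calculation therefore belongs to the strength endpoint, as do the primary research question and the planned test. It gives no power for a 1-month pain response.

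**The case against.** The strongest reply is that silence in the Procedure does not prove that an item is not collected. The plan points to a report form for all data before and after the procedure, and that form is not among the documents. The Procedure text is also plainly not exhaustive: the Secondary outcomes section expects day-1 NRS and medication use, yet the description of the day-1 call names neither. This stands, and it limits the claim to what the Procedure schedules. It does not remove the point, because a form does not create a visit, and no section says when, how or by whom a 1-month assessment is made.

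A reader might go further and infer any of the following. The documents do not support them:

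- *All the missing baselines are lost for good.* This is firm for NDI-5 and for separate neck and arm NRS scores. Baseline medication use is recorded, so MQS III and morphine equivalents may be recoverable.
- *Every listed outcome is a 1-month outcome.* Only the NRS response is tied to 1 month. The others have no time point, which is a gap in its own right.
- *The second null hypothesis cannot be tested.* It speaks of short-term effects, and three of its four domains have day-1 outcomes.
- *The trial's main result is compromised.* The powered 30-minute strength comparison is unaffected.

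It can also be argued that the simpler repair is to cut the Data Analysis Plan back to the existing schedule. That is consistent with the documents and is kept below as the alternative.

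**Conclusion.** The point holds as an inconsistency between sections that must be resolved before further participants are injected. Under the Procedure as written, the outcomes in the Data Analysis Plan have no scheduled follow-up after day 1 for any of up to 104 participants, and one of those outcomes is labelled primary. The 30% NDI-5 response has no pre-injection score, and the neck and arm NRS response may have no matching one; neither can be obtained after injection. PGIC, satisfaction and surgery need only a follow-up contact.

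This rests on the Procedure being the operative schedule and on the unseen report form not adding both the instruments and a 1-month contact. If the form already carries a pre-injection NDI-5, the irreversible part for NDI-5 falls away, but the unscheduled follow-up and the missing time points remain.

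**What to change.** **Reconcile the sections.** Keep 30-minute strength as the single primary outcome, since it matches the primary research question, the Power Analysis and the Statistical analysis section. Make the 1-month outcomes secondary in the Data Analysis Plan.

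**Before injection, in the Procedure.** For both groups, add the NDI-5, separate neck and arm NRS scores, and an itemised medication record (drug, dose, frequency) sufficient to score MQS III and daily morphine equivalents.

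**After day 1, in the Procedure.** Add one telephone or email contact at 1 month with a stated window. Collect neck and arm NRS, NDI-5, medications, PGIC, satisfaction and any spine surgery since injection.

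**In the Data Analysis Plan.** Give every outcome its time point, and count surgery up to the 1-month contact.

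**Participants already injected without a baseline NDI-5.** Report the 1-month NDI-5 score between randomised groups, which needs no baseline, and do not report the 30% response for them.

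**Alternative.** If no 1-month contact will be made, delete the outcomes that cannot be collected and say how global impression of change will be assessed, or drop it from the second hypothesis.

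**Cost.** A protocol and report-form amendment, a few more minutes before injection, and one more contact per participant through a channel already used on day 1. No extra participants or procedures are needed.
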